8.3. Patients Lost to Follow-Up

A patient will be considered lost to follow-up if he or she repeatedly fails to return for scheduled visits and is unable to be contacted by the study site. Site personnel are expected to make diligent attempts to contact patients and/or study partners who fail to return for a scheduled visit or were otherwise unable to be followed up by the site.

Site personnel, or an independent third party, will attempt to collect the vital status of lost-to-follow-up patients within legal and ethical boundaries for all patients randomized, including those who did not get investigational product. Public sources may be searched for vital status information. If vital status is determined, this will be documented and the patient will not be considered lost to follow-up.

Lilly personnel will not be involved in any attempts to collect vital status information.

9. Study Assessments and Procedures

Section 2 lists the Schedule of Activities, with the study procedures and their timing (including tolerance limits for timing).

Appendix 2 lists the laboratory tests that will be performed for this study.

Unless otherwise stated in the subsections below, all samples collected for specified laboratory tests will be destroyed within 60 days of receipt of confirmed test results. Certain samples may be retained for a longer period, if necessary, to comply with applicable laws, regulations, or laboratory certification standards.

9.1. Efficacy Assessments

9.1.1. Primary Efficacy Assessments

Alzheimer's Disease Assessment Scale—Cognitive subscale (ADAS-Cog; Rosen et al. 1984). The ADAS is a rater-administered instrument that was designed to assess the severity of the dysfunction in the cognitive and noncognitive behaviors characteristic of persons with AD; ADAS-Cog refers to the cognitive subscale which was originally designed with 11 items (the ADAS-Cog₁₁). An expanded version that includes 3 additional items more sensitive in patients at earlier stages of AD, the ADAS-Cog₁₄ (Mohs et al. 1997), will be used as a primary efficacy measure. It consists of 14 items assessing areas of cognitive function most typically impaired in AD: orientation, verbal memory, language, praxis, delayed free recall, digit cancellation, and maze-completion measures. The ADAS-Cog₁₄ allows better discrimination of differences among milder AD patients than the ADAS-Cog₁₁. The ADAS-Cog₁₄ scale ranges from 0 to 90, with higher scores indicating greater disease severity.

Note: The administration of the ADAS-Cog will be recorded (audio only) at each administration for quality review purposes except where prohibited by local laws and regulations. The ADAS-Cog and Alzheimer's Disease Cooperative Study-Mild Cognitive Impairment–Activities of Daily Living Inventory (ADCS-MCI-ADL) must be performed by 2 different qualified raters.

9.1.2. Secondary Efficacy Assessments

Alzheimer's Disease Cooperative Study—Activities of Daily Living Inventory for Mildly Cognitively Impaired (ADCS-MCI-ADL; Pedrosa et al. 2010). The ADCS-MCI-ADL is a functional evaluation scale for MCI patients, based on information provided by an informant (in this case the study partner), that describes the performance of patients in several ADLs. It was adapted from the original ADCS-ADL scale, which was constructed to evaluate patients with dementia in the Alzheimer's Disease Cooperative Study, as a measure of the AD patients' performance in activities of daily living (ADLs) (Galasko et al. 1997). An 18-item ADCS-MCI-ADL was developed alongside the original ADCS-ADL, but more recently a 24-item version (Pedrosa et al. 2010) was developed to incorporate additional items considered appropriate to the MCI population, which has been shown to better distinguish between healthy subjects and people with MCI. This study will use the 24-item version. The range for this scale

is 0 to 69, with lower scores indicating greater disease severity. For each of the specific items, the informant is first asked if the patient attempted the ADL during the past 4 weeks. If the patient did attempt the ADL, the informant is asked to rate the patient's performance level based on a set of performance descriptions. Scores for each item and the overall score for the tool are calculated.

Note: The administration of the ADCS-MCI-ADL will be recorded (audio only) at each administration for quality review purposes except where prohibited by local laws and regulations. The ADAS-Cog₁₄ and ADCS-MCI-ADL must be performed by 2 different qualified raters.

Mini-Mental State Examination (MMSE; Folstein et al. 1975). The MMSE is a brief instrument used to assess cognitive function. The instrument is divided into 2 sections. The first section measures orientation, memory, and attention. The maximum score for the first section is 21. The second section tests the ability of the patient to name objects, follow verbal and written commands, write a sentence, and copy figures. The maximum score for the second section is 9. The range for the total MMSE score is 0 to 30.

Montreal Cognitive Assessment (MoCA; Nasreddine et al. 2005). The MoCA is a brief 30-point cognitive screening test developed with high sensitivity and specificity for detecting MCI in patients who perform in the normal range on the MMSE. Compared to the MMSE, the MoCA uses more numerous and demanding tasks to assess executive function, higher level language abilities, memory, and complex visuospatial processing.

Note: The administration of the MoCA will be recorded (audio only) at each administration for quality review purposes except where prohibited by local laws and regulations. The MMSE and MoCA should not be administered in succession (that is, at least one other scale should be administered in between) and if possible should be done by different raters.

Neuropsychiatric Inventory (NPI; Cummings et al. 1994). The NPI is a tool for assessing psychopathology in patients with dementia and other neurologic disorders. Information is obtained from an informant familiar with the patient's behavior (often a caregiver; in this study, the study partner). A screening question assays each subarea of the NPI—delusions, hallucinations, agitation, apathy, anxiety, depression, euphoria, irritability, disinhibition, and aberrant motor behavior. Two questions inquire about neurovegetative changes, including alterations in appetite and nighttime behavior disturbances. If the answer to the screening question is no, no further questions are pursued. If the answer is yes, subquestions are asked and ratings of the frequency and severity of the behavior are made by the informant through the use of scales with anchor points. The distress induced in the informant by each behavior is also rated. Scores for each subscale, the total tool, informant distress associated with each behavior, and total informant distress are computed. The NPI standard version consists of 10 items with informant distress scale and 2 neurovegetative questions. Four subscales can be defined based on a previously reported factor analysis: Mood (depression, anxiety, nighttime behavior, appetite, and irritability); Psychosis (delusions, hallucinations, and agitation); Frontal (euphoria and disinhibition); and Other (apathy and aberrant motor behavior) (Frisoni et al. 1999).

Clinical Dementia Rating Scale (CDR-SB; Berg et al. 1992). The CDR is a semi-structured interview performed with the patient and informant that provides an index of global functioning. The informant is queried about the patient’s memory, orientation, judgment and problem solving, community affairs, home and hobbies, and personal care. The patient’s memory, orientation, judgment, and problem-solving ability are assessed. By assigning a severity score for each of the 6 domains, a total score known as sum of boxes is obtained—hence the abbreviation, CDR-SB.

Resource Utilization in Dementia—Lite questionnaire (RUD-Lite; Wimo et al. 1998). The RUD-Lite is an abbreviated version of the Resource Utilization in Dementia (RUD) scale designed to assess the healthcare resource utilization of patients and their caregivers (or in this case, study partners) and to determine the level of formal and informal care attributable to AD. The data are collected through a structured interview. Information on both study partners (caregiving time and work status) and patients (accommodation and healthcare resource utilization) is gathered from the baseline and final assessment interviews. Study partners will be asked to provide data on time spent assisting patients’ basic ADLs such as using the toilet, eating, dressing, grooming, walking, and bathing; assisting patients’ instrumental ADLs such as shopping, cooking, housekeeping, laundry, transportation, taking medication, and managing finances; and providing supervision. The resource utilization quantified by the RUD-Lite can be used for calculating cost offsets and in cost-effectiveness models.

Note that as of 2016, only the full RUD is supported by its copyright owners, such that users who wish to administer a shorter version must pull out questions from the RUD. Study LZBE is administering the short version of the RUD once formally known as the RUD-Lite and will continue to use the name “RUD-Lite” for consistency with other solanezumab protocols that have administered this scale.

EuroQoL-5D Proxy Version (EQ-5D; Kind 1996). The EQ-5D is a standardized instrument used to measure overall health status and is applicable to a wide range of health conditions and treatments. It provides both a descriptive profile and a single index value for health status. The 5D in the name refers to the 5-dimensional classification system for health states used in the instrument. Each dimension (mobility, self-care, usual activities, pain/discomfort, and anxiety/depression) has 5 levels of severity (no, slight, moderate, severe, and extreme problems). Scores on individual dimensions are recorded, as is a total score that sums the individual dimension scores. A visual analog scale also assesses the informant’s impression of the patient’s overall health state. Reliability and validity of the proxy version for use with an AD population have been demonstrated (Jönsson et al. 2006; Naglie et al. 2006). Scores can be converted into weighted health state preferences for quality-adjusted life year models.

Quality of Life in Alzheimer’s Disease (QoL-AD; Logsdon et al. 2002; Thorgrimsen et al. 2003). The QoL-AD is a disease-specific measure of quality of life for an AD population. It includes 13 items, each rated on a 4-point scale. Summing the items provides an overall score to index the patient’s quality of life. The QoL-AD is administered to the patient by a rater and asks the patient to provide ratings on mood, relationships, memory, finances, and so on. The patient’s study partner also is asked to complete the measure. Reliability and validity in samples of AD patients and their caregivers have been demonstrated.

Repeatable Battery for the Assessment of Neuropsychological Status (RBANS; Randolph et al. 1998). The RBANS is a collection of 12 subtests representing 5 neurocognitive domains: Immediate Memory, Visuospatial/Constructional, Language, Attention, and Delayed Memory. The raw scores from each subtest within a domain are converted to a summary score, or Index Score that summarizes the patient's overall level of performance on this measure. Version A of the scale will be used at baseline and endpoint; Version B will be used at the 12-month visit.

Free and Cued Selective Reminding Test (FCSRT; Grober and Buschke 1987). The FCSRT is a neuropsychological test of memory under conditions that control attention and cognitive processing in order to obtain an assessment of memory unconfounded by normal age-related changes in cognition. Both a word and picture version are available; this study will use the picture version. The FCSRT has previously demonstrated sensitivity in prediction of decline from MCI to AD dementia in other studies (Amieva et al. 2008; Dubois et al. 2010), and in predicting dementia in previous cohort studies from the Baltimore Longitudinal Study of Aging (Grober et al. 2008) and the Einstein Study of Aging (Derby et al. 2013).

Note: The administration of the FCSRT will be recorded (audio only) at each administration for quality review purposes except where prohibited by local laws and regulations.

Functional Activities Questionnaire (FAQ; Pfeffer et al. 1982). The FAQ is a rater-administered instrument directed at the caregiver (in this case, the study partner) that assesses perceived ability in performing instrumental everyday activities thought to be especially cognitively complex (for example, financial management, shopping, playing games, food preparation, traveling, keeping appointments, keeping track of current events, and understanding media). Each of the 10 items offers 6 response alternatives, varying in level of dependence and familiarity of the task, which are recorded so that each item receives a score ranging from 1 (*complete independence*) to 4 (*complete dependence*). The sum of 10 items provides an overall assessment of perceived functional ability. A growing literature supports the FAQ as a measure sensitive to changes in AD patients at the earlier end of the disease spectrum (Tabert et al. 2002; Teng et al. 2010).

Note: The administration of the FAQ will be recorded (audio only) at each administration for quality review purposes except where prohibited by local laws and regulations.

Florbetapir PET scan. Change in amyloid burden (as assessed by florbetapir binding) will be compared in solanezumab- and placebo-treated patients. See [Appendix 4](#) for information about radiation dose.

¹⁸F AV-1451 PET scan. Changes in tau (as assessed by ¹⁸F AV-1451 binding) will be collected as part of an addendum.

9.1.3. Appropriateness of Assessments

Efficacy. The ADAS-Cog is a well-accepted measure of cognitive functioning in patients with mild to moderate AD; the 14-item version is considered more sensitive in milder AD. The ADCS-MCI-ADL is also well recognized as a measure of functional abilities in patients with

prodromal AD/MCI. A growing literature supports the FAQ as a measure sensitive to changes in milder AD populations. Additional descriptions and references supporting use of these and other scales are provided in Sections 9.1.1 and 9.1.2.

Safety. Safety measures used in this study are all well established.

9.2. Safety Evaluations

Investigators are responsible for monitoring the safety of patients who have entered this study and for alerting Lilly or its designee to any event that seems unusual, even if this event may be considered an unanticipated benefit to the patient.

The investigator is responsible for the appropriate medical care of patients during the study.

Investigators must document their review of each laboratory safety report.

The investigator remains responsible for following, through an appropriate health care option, AEs that are serious or otherwise medically important, considered related to the investigational product or the study, or that caused the patient to discontinue the investigational product before completing the study. The patient should be followed until the event resolves, stabilizes with appropriate diagnostic evaluation, or is reasonably explained. The frequency of follow-up evaluations of the AE is left to the discretion of the investigator.

9.2.1. Adverse Events

A clinical study AE is any untoward medical event associated with the use of a drug or drug delivery system in humans, whether or not it is considered related to a drug or drug delivery system.

Lilly has standards for reporting AEs that are to be followed regardless of applicable regulatory requirements that may be less stringent.

Lack of drug effect is not an AE in clinical studies, because the purpose of the clinical study is to establish treatment effect.

Study site personnel will record the occurrence and nature of each patient's preexisting conditions, including clinically significant signs and symptoms of the disease under treatment in the study.

After the ICF is signed, study site personnel will record via CRF the occurrence and nature of each patient's preexisting conditions, including clinically significant signs and symptoms of the disease under treatment in the study. In addition, site personnel will record any change in the condition(s) and any new conditions as AEs. Investigators should record their assessment of the potential relatedness of each AE to investigational product and/or protocol procedure via CRF.

The investigator will interpret and document whether or not an AE has a reasonable possibility of being related to study treatment, PET tracers, study device, or a study procedure, taking into account the disease, concomitant treatment, or pathologies.

A “reasonable possibility” means that there is a cause and effect relationship between the investigational product, PET tracers, study device, and/or study procedure and the AE.

The investigator answers yes/no when making this assessment.

Planned surgeries and nonsurgical interventions should not be reported as AEs unless the underlying medical condition has worsened during the course of the study.

If a patient’s investigational product is discontinued as a result of an AE, study site personnel must report this to Lilly or its designee via CRF, clarifying if possible, the circumstances leading to any dosage modifications or discontinuations of treatment.

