9.2.2. Serious Adverse Events

An SAE is any AE from this study that results in one of the following outcomes:

- death
- initial or prolonged inpatient hospitalization
- a life-threatening experience (that is, immediate risk of dying)
- persistent or significant disability/incapacity
- congenital anomaly/birth defect
- considered significant by the investigator for any other reason: important medical events that may not result in death, be life-threatening, or require hospitalization may be considered serious, based upon appropriate medical judgment

Although all AEs after signing the ICF are recorded in the CRF, SAE reporting begins after the patient has signed the ICF and has received investigational product. However, if an SAE occurs after signing the ICF, but prior to receiving investigational product or PET imaging, it needs to be reported ONLY if it is considered reasonably possibly related to study procedure.

Study site personnel must alert Lilly or its designee of any SAE within 24 hours of investigator awareness of the event via a sponsor-approved method. If alerts are issued via telephone, they are to be immediately followed with official notification on study-specific SAE forms. This 24-hour notification requirement refers to the initial SAE information and all follow-up SAE information.

Pregnancy (during maternal or paternal exposure to investigational product) does not meet the definition of an AE. However, to fulfill regulatory requirements any pregnancy should be reported following the SAE process to collect data on the outcome for both mother and fetus.

Investigators are not obligated to actively seek AEs or SAEs in patients once they have discontinued and/or completed the study (the patient summary CRF has been completed). However, if the investigator learns of any SAE, including a death, at any time after a patient has been discharged from the study, and he/she considers the event reasonably possibly related to the study treatment or study participation, the investigator must promptly notify Lilly.

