9.2.2.1. Suspected Unexpected Serious Adverse Reactions

Suspected unexpected serious adverse reactions (SUSARs) are serious events that are not listed in the IB and that the investigator identifies as related to investigational product or procedure. United States 21 CFR 312.32 and European Union Clinical Trial Directive 2001/20/EC and the associated detailed guidances or national regulatory requirements in participating countries require the reporting of SUSARs. Lilly has procedures that will be followed for the recording and expedited reporting of SUSARs that are consistent with global regulations and the associated detailed guidances.

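### Protocol 9.2.1 defines a reasonable possibility of relatedness as an actual cause-and-effect relationship; read literally, this raises the threshold for four safety routes that depend on the relatedness answer

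*Protocol*

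**What the plan says.** Protocol Section 9.2.1 describes the relatedness judgement in four places.

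- Investigators are told what to record: "Investigators should record their assessment of the potential relatedness of each AE".
- The question they must interpret and document is "whether or not an AE has a reasonable possibility of being related to study treatment", or to PET tracers, a study device or a study procedure, with the disease, other treatment and other pathology taken into account.
- The key phrase is then defined. It "means that there is a cause and effect relationship between the investigational product, PET tracers, study device, and/or study procedure and the AE".
- The response is binary: "The investigator answers yes/no when making this assessment".

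Later sections use the judgement. In 9.2.2, for an SAE after consent but before investigational product or PET imaging, "it needs to be reported ONLY if it is considered reasonably possibly related to study procedure". Also in 9.2.2, for an SAE that the investigator learns of after discharge, the duty arises if "he/she considers the event reasonably possibly related to the study treatment or study participation, the investigator must promptly notify Lilly". In 9.2.2.1, SUSARs are serious unlisted events "that the investigator identifies as related to investigational product or procedure". In 9.2, relatedness is one of several alternative grounds for following an AE until it resolves, stabilises or is explained.

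**The concern.** The question and its definition sit next to each other and set different thresholds. The question, like the instruction to record potential relatedness, can be answered yes when causation is plausible. The definition carries no *may*, *suspected* or *potential*, so taken at its word it is met only when causation exists. There is no middle category for uncertainty.

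An investigator who follows the definition would answer no for an event that might have been caused by the drug or a procedure but cannot be shown to have been. An investigator who follows the question would answer yes for the same event. What is at stake is how certain serious events are classified and whether they are passed on, and whether sites do this consistently.

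**Working it through.** There is no figure to reproduce and no arithmetic that decides the point. The check is to compare the wording within 9.2.1, and then to trace where the answer is used and where it is not.

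**Step 1: is there a conflict within 9.2.1?** The recording instruction speaks of potential relatedness and the question speaks of a reasonable possibility. Both are possibility standards. The definition states that a causal relationship exists. Two of the three statements set a lower threshold than the third, and the third is the one that claims to define the term.

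**Step 2: does anything else resolve it?** No other section of the protocol defines the phrase or says how to answer when causality is uncertain. The abbreviations and definitions in Appendix 1 do not cover it. The SAP does not address relatedness.

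**Step 3: which rules depend on the answer?**

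| Route | Section | Consequence of an over-strict no |
|---|---|---|
| SUSAR classification | Protocol 9.2.2.1 | An unlisted serious event is not identified as a SUSAR. If it occurred on study after dosing, the sponsor already has it as an SAE |
| SAE before investigational product or PET imaging | Protocol 9.2.2 | No SAE report is required; the event is still in the CRF as an AE |
| SAE learned of after discharge | Protocol 9.2.2 | No duty to notify is triggered; the event may not reach the sponsor |
| Continued follow-up of an AE | Protocol 9.2 | Decisive only for AEs that are not serious, have no other medical importance and did not lead to stopping investigational product |

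**Step 4: which rules do not depend on it?**

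- All AEs after consent go into the CRF (Protocol 9.2.2).
- Any SAE on study after dosing is notified within 24 hours, whatever the relatedness answer (Protocol 9.2.2).
- The SAP defines a TEAE by timing relative to first infusion and Visit 301. Its AE overview and listing apply no relatedness filter (SAP 6.7.2).

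**Step 5: how large is the exposure?** The protocol was written for about 2450 patients. The SAP (6.1) records that the study was discontinued with 26 randomized subjects, so the wording applied to about 26/2450 = 1.1% of the planned number. Neither document gives a rate of relatedness answers, of pre-dose SAEs or of post-discharge SAEs, so no count of affected events can be derived.

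**The case against.** The strongest reply is that the definition can be read as saying what the possibility is a possibility *of*, namely causation, without asking for proof. The surrounding text supports that reading: it speaks of potential relatedness and asks the investigator to weigh competing explanations. Section 9.2.2 also says *reasonably possibly related*, which is not the exact defined phrase, so carrying the strict definition over to it takes a further step. This stands in part. No sentence tells investigators to answer no when unsure, so that outcome follows from a literal reading and is not an instruction. But a definition that needs its context to correct it leaves room for sites to differ, and a binary answer gives them nowhere to record doubt.

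The second reply is that other safeguards exist. Investigators must alert the sponsor to unusual events (9.2). Special-interest clusters are monitored and cerebro-cardiovascular events are adjudicated by a blinded external committee (9.2.2.2). The sponsor and a data monitoring committee were to review safety data periodically (9.3.8), although SAP 6.8 plans no committee meeting after the early stop. The SUSAR section states that the sponsor's procedures are consistent with global regulations. These points limit the consequences. They do not remove the dependence of SUSAR status on the investigator's answer, or create a separate relatedness-free duty specific to post-discharge SAEs.

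Four stronger inferences are tempting, and the documents do not support them:

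- *SAEs in general fail to reach the sponsor.* On-study SAEs after dosing go within 24 hours regardless, and pre-dose events are in the CRF. Only post-discharge SAEs may be missed altogether.
- *Uncertain causality is the usual case.* Neither document gives any data on this.
- *The answer controls follow-up of AEs.* It is one trigger among several and decides only the residual group in the table.
- *The safety tables are distorted.* The SAP's TEAE outputs do not use relatedness.

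**Conclusion.** The point holds in bounded form. Section 9.2.1 contradicts itself on the threshold for relatedness, and nothing else in the documents settles which statement governs. On a literal reading the threshold is too high for the question asked, and the four routes above inherit it. The most direct is SUSAR classification, because 9.2.2.1 rests on the investigator's own identification of relatedness. The most consequential for completeness is the post-discharge rule, because a no there can mean that the sponsor is not told.

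The size cannot be quantified, and with 26 subjects randomized the realised effect is small. The conclusion assumes that at least some investigators would apply the definition as written. The documents do not show what CRF guidance or training sites received, and either could have reduced the effect or made it worse. The point is worth correcting because the term governs safety reporting and the correction is cheap. It does not call any planned safety summary into question.

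**What to change.** In the defining sentence of Protocol Section 9.2.1, change *there is* to *there may be*, so that a reasonable possibility means that there may be a causal relationship. The definition then agrees with the question that precedes it, with the instruction to record potential relatedness, and with the wording of the two SAE rules in 9.2.2. Any CRF completion guidance that repeats the definition should be changed to match.

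The cost is one phrase plus that guidance. The downside is that somewhat more events will be classed as related. Endpoints, sample size, randomization and the SAP's outputs are untouched. As the trial has ended early, the practical use of the change is in any later protocol that carries the same sentence.
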